8.3 NONCOMPLIANT SUBJECTS

Subjects who are found to be noncompliant will be queried as to the reason for their noncompliance. If noncompliance results from study product problems, full interviews will be conducted by the investigator to determine the nature and severity of the problem and an adverse event will be recorded. Subjects who are noncompliant will be released from their study participation and their last visit data carried forward.

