9.1 COMPLETED, DISCONTINUED OR INCOMPLETE SUBJECTS

A completed subject is a subject who has satisfied all study entry criteria and completed the 2-week study. For any subject who has started study and terminates the study prematurely, efforts will be made to obtain final evaluations of clinical status. Reasonable efforts will be made to contact any subject lost to follow-up during the course of the study in order to complete assessments and retrieve any outstanding data and clinical supplies. The investigator will choose the description that best describes the status of the subject at termination.

1. Subject completed the 2-week study period

OR INCOMPLETE/DISCONTINUED DUE TO:

- 2. Contact dermatitis
- 3. Adverse experience
- 4. Serious adverse experience
- 5. Pregnancy
- 6. Protocol violation
- 7. Subject withdrew consent
- 8. Subject lost to follow-up
- 9. Other

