12. STATISTICAL METHODS

Along with descriptive statistics (means, standard deviations and percentages), investigator and subject ordinal nonparametric results will be analyzed using Wilcoxon signed rank test and sign test for paired comparison at different time points. The noninvasive parametric results will be analyzed using paired t-test. Changes will be considered significant at the alpha level of 0.05.

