12.3 DROP-OUT (PRODUCT TOLERABILITY) ASSESSMENT

Subjects who discontinue will be queried as to any side effects experienced by the study products.

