- 4. Subjects who have demonstrated a previous hypersensitivity reaction to any of the ingredients of the study products.
- 5. Subjects, who are pregnant, breast feeding, or planning a pregnancy.
- 6. Subjects with clinically significant unstable medical disorders.
- 7. Subjects who are unwilling or unable to comply with the requirements of the protocol.
- 8. Subjects who have history of a psychological illness or condition that would interfere with their ability to understand and follow the requirements of the study.
- 9. Subjects who are currently participating in any other clinical study.
- 10. Subjects with any planned surgeries and/or invasive medical procedures during the course of the study.
- 11. Subjects who currently or frequently use high doses of anti-inflammatory drugs for a defined medication condition. Aspirin use should not exceed 2 tablets (650 mg) per day.
- 12. Subjects currently receiving any anticancer, immunosuppressive treatments/ medications (e.g., azathioprine, belimumab, cyclophosphamide, Enbrel, Imuran, Humira, mycophenolate mofetil, methotrexate, prednisone, Remicade, Stelara.), or radiation as determined by the initial paperwork.
- 13. Subjects with a history of immunosuppression/immune deficiency disorders (including (HIV infection or AIDS) or currently using immunosuppressive medications (e.g., azathioprine, belimumab, cyclophosphamide, Enbrel, Imuran, Humira, mycophenolate mofetil, methotrexate, prednisone, Remicade, Stelara) and/or radiation as determined by study documentation.

All inclusion criteria must be met and none of the exclusion criteria. Circle any inclusion criteria that are not met and any exclusion criteria that are met and declare the subject a screening failure. I certify all inclusion criteria have been met and none of the exclusion criteria have been met.

[name] Primary Investigator Date

INVESTIGATOR TOLERABILITY ASSESSMENT

RIGHT CHEEK

Visits	Baseline	24 Hours	Week 1	Week 2
Dryness	01234	01234	01234	01234
Erythema	01234	01234	01234	01234
Scaling	01234	01234	01234	01234
Irritation	01234	01234	01234	01234

LEFT CHEEK

Visits	Baseline	24 Hours	Week 1	Week 2
Dryness	01234	01234	01234	01234
Erythema	01234	01234	01234	01234
Scaling	01234	01234	01234	01234
Irritation	01234	01234	01234	01234

0=none, 1=minimal, 2=mild, 3=moderate, 4=severe

SUBJECT TOLERABIILTY ASSESSMENT

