Please let us know if you are experiencing any of these problems. Please use the following scale: 0=none, 1=minimal, 2=mild, 3=moderate, 4=severe. A lower number means you do not have the problem. Circle your correct response. Please rate both your cheeks separately.

Ask the study staff if you have any questions.

RIGHT CHEEK

Visits	Baseline	24 Hours	Week 1	Week 2
Dryness	01234	01234	01234	01234
Tightness	01234	01234	01234	01234
Stinging	01234	01234	01234	01234
Itching	01234	01234	01234	01234
Burning	01234	01234	01234	01234

LEFT CHEEK

Visits	Baseline	24 Hours	Week 1	Week 2
Dryness	01234	01234	01234	01234
Tightness	01234	01234	01234	01234
Stinging	01234	01234	01234	01234
Itching	01234	01234	01234	01234
Burning	01234	01234	01234	01234

NONINVASIVE ASSESSMENTS

	Baseline	24 Hours	Week 1	Week 2
TEWL Right Cheek				
TEWL Left Cheek				
Corneometry Right Cheek				
Corneometry Left Cheek				

ADVERSE EVENT

Did the subject experience any adverse event? Yes or No *If yes, list below:

Adverse Event	1	2
Start Date mm/dd/yy		
Stop Date mm/dd/yy		
Ongoing*		
Frequency ¹		
Severity ²		
Relation to Study Med ³		
Action Taken ⁴		
Outcome ⁵		
Serious (Y/N)		
¹ Frequency ² Severity 1=Continuous 1=Mild 2=Intermittent 2=Moderate 3=Isolated 3=Severe	³ Relation to Study Med 1=Not related 2=Possible 3=Probable 4=Definite	⁴ Action Taken (insert all codes that apply) 1=None 2=Study drug discontinued 3=Non-drug therapy 4=New OTC or R _x drug added

⁵Outcome

1=Resolved

2=Improved

3=Stabilized

4=Ongoing

5=Worsened

6=Lost to follow-up

*Check only if the adverse event is ongoing when subject completes/exits the study.

**Refer to the protocol for definitions of severity and relationship to study product.

Final Subject Status				
The s	ubject completed the study. Date Completed: Month Day	Year		
The streason:	ubject discontinued the study prematurely due to the following O	DNE		
	Date Discontinued: Month Day	Year		
discontinua	Adverse event, including intercurrent illness, which required study tion (specify) Protocol violation (specify)	-		
	Lost to follow-up Subject decision/withdrawal of consent			
	Other (specify)	?		

Investigator's State	ement:
information record	pages of this case report form. To the best of my knowledge, the led on the case report form is a complete and accurate record of ment course during the study.
Signature	Printed Name
Date Signed:	nth Day Year

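### Section 8.3 can let values from before a reaction stand for later visits when a subject stops for a product problem and misses the next scheduled visit

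*Combined protocol and SAP*

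**What the plan says.** Section 8.3 gives the only rule for missing later data: "Subjects who are noncompliant will be released from their study participation and their last visit data carried forward". The sentence before it brings product-related stopping under the same heading: "If noncompliance results from study product problems, full interviews will be conducted by the investigator", and an adverse event is then recorded.

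Tolerability grades, corneometry and TEWL are taken at baseline, 24 hours, week 1 and week 2 (sections 2 and 8.1). In Appendix I, the form headed "INVESTIGATOR TOLERABILITY ASSESSMENT", the subject form ("Please rate both your cheeks separately") and the noninvasive form have columns for those four visits only.

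For early terminations, section 9.1 says "efforts will be made to obtain final evaluations of clinical status". It does not say what the evaluation contains, where it is recorded, or whether it replaces the carried value. Section 12.3 adds a query: "Subjects who discontinue will be queried as to any side effects experienced by the study products". Section 12 says "investigator and subject ordinal nonparametric results will be analyzed using Wilcoxon signed rank test and sign test for paired comparison at different time points" and assigns the paired t-test to the instrument readings. It does not mention carry-forward or any other treatment of missing values.

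**The concern.** Only one side of the face receives product, and subjects with the worst reactions are the most likely to stop. If such a subject stops between visits and does not come to the next one, the carried values date from before the reaction. The subject then counts as not worse on the treated side. If the last visit showed no difference between sides, the pair is a tie and contributes nothing to the sign or signed rank test.

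The error tends to run toward the conclusion the study seeks in section 4. Because section 8.3 covers all last visit data, it reaches corneometry (primary) and TEWL (secondary) as well as the supporting tolerability results.

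**Working it through.** **Which values are carried.** The plan states no figure on this point to reproduce. From the visit schedule, for a subject who reacts, stops and does not return:

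- Onset between baseline and 24 hours: baseline values stand for all later visits.
- Onset between 24 hours and week 1: 24-hour values stand for weeks 1 and 2.
- Onset after week 1: week 1 values stand for week 2.

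**Assumed example.** Inputs from the documents: n = 50 (section 12.1) and two-sided alpha 0.05 (section 12.2). Assumptions: 6 subjects react on the treated side only, between 24 hours and week 1; all other pairs are tied; the sides are compared with each other (section 12 does not state the pairing). With k reactors graded and none in the other direction, the exact two-sided p is 2 × 0.5^k, for the sign test and for the smallest exact signed rank p. The large-sample Wilcoxon ranges cover all patterns of grade differences 1 to 4.

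| Graded as worse | Exact p | Wilcoxon, uncorrected | Wilcoxon, continuity-corrected |
|---|---|---|---|
| 6 v 0 | 0.031 | 0.014–0.027 | 0.020–0.035 |
| 5 v 0 | 0.0625 | 0.025–0.042 | 0.037–0.058 |
| 4 v 0 | 0.125 | 0.046–0.068 | 0.072–0.100 |
| 3 v 0 | 0.25 | 0.083–0.109 | 0.149–0.181 |

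All six graded: 6/50 = 12% (Clopper-Pearson 95% CI 4.5% to 24.3%), below 0.05 under every version. Three stop and their 24-hour grades are carried: 3/50 = 6% (1.3% to 16.5%), above 0.05 under every version. If only one or two stop, the result depends on the version of the test. Leaving the three out instead gives 3/47 (1.3% to 17.5%), which is nearly the same.

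**Corneometry and TEWL.** If k stoppers each have a true side difference of D units and carry a difference of zero, the mean side difference is diluted by kD/50. For k = 3 and assumed D of 5, 10 or 20, that is 0.3, 0.6 or 1.2 units. The documents give no standard deviation, so this cannot be turned into a change in power.

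**Simulation on assumed rates** (10,000 runs, n = 50). The assumptions are 15% treated-side reactors with onset after 24 hours; reaction grade 1, 2 or 3 with probability 0.4, 0.4, 0.2; and 5% one-grade background worsening per side per visit. Chance of detecting harm at week 2:

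| Reactors who stop | Handling | Exact sign | Wilcoxon, uncorrected |
|---|---|---|---|
| none | – | 0.505 | 0.755 |
| 25% | carry-forward | 0.304 | 0.533 |
| 50% | carry-forward | 0.140 | 0.288 |
| 75% | carry-forward | 0.041 | 0.095 |
| 50% | exit grade used for all | 0.505 | 0.754 |
| 50% | half of the stoppers graded at exit, the rest missing | 0.314 | 0.546 |

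A separately coded run on the same assumptions gave Wilcoxon detection of 76%, 56%, 30% and 10% for the first four rows. With half of the reactors stopping and none graded, leaving them missing gave 31% against 30% with carry-forward. At 2% reactors, detection was about 4% with no stops and 3% with half stopping.

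**Counting stoppers as worse.** With no product effect and an assumed 4% who stop and blame the product without a reaction, the false-positive rate for harm (Wilcoxon) is 0.024 under carry-forward and 0.108 if each is counted as worse on the treated side.

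**The case against.** The strongest reply is that the route is narrow. Compliance is judged from the diary (section 8.2) and checked at 24 hours, week 1 and week 2 (section 2), when grading and instrument readings are also done. Noncompliance found there normally comes with a current assessment. A reactor may also be discontinued under section 9.1 for contact dermatitis or an adverse experience, where no carry-forward is stated. Subjects withdrawn for an adverse event are followed to outcome (section 11.2.1), and section 9.1 promises efforts to reach those lost to follow-up and complete their assessments. Section 11.1 calls skin irritation rare. All of this stands and limits the reach.

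It does not close the gap. No section says that a final evaluation replaces the carried value, and the forms have no column for one. The adverse event form ("Did the subject experience any adverse event? Yes or No") has no field for side and no 0–4 item grades. The treated side can usually be inferred from the randomization code (section 10.6), but the event still does not enter the comparison of sides. For reactors discontinued under section 9.1 the plan gives no rule for later visits.

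A reader might infer that the plan loses reactions altogether, or that every noncompliant subject is scored at a value from before the reaction. The documents do not support either: an adverse event is recorded, and a subject who attends the next visit is assessed there, although a reaction may have partly faded by then.

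**Conclusion.** The point holds as a limited gap in a written rule. Values from before a reaction can stand for later visits when a subject stops for a product problem between visits, is handled under section 8.3, and is not assessed again. The likely direction is toward hiding treated-side harm, in the tolerability results and in corneometry and TEWL.

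The size is not known. With no stops there is no effect. If reactions are as rare as section 11.1 suggests, for example 1 of 50, the count changes but the test result does not. The drop from 12% to 6% and the detection figures rest on assumed reaction, stopping and background rates and on pairing side with side. A reader might also infer that the primary conclusion would be reversed. The documents give no corneometry variance or effect size, so that cannot be claimed. The change is worth making because it is cheap and the rule fails in exactly the subjects who matter for tolerability.

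**What to change.** 1. In sections 8.3 and 12, state that for any subject who stops or is released for a product problem or adverse event, the final evaluation that section 9.1 already seeks includes tolerability grading of both sides by the blinded investigator and by the subject, plus corneometry and TEWL on both cheeks.
2. Add a dated Exit column to the investigator, subject and noninvasive forms. Use the exit values, not the last scheduled visit, for the remaining visits in the tolerability, corneometry and TEWL analyses.
3. If no exit evaluation is obtained, do not carry values from before the reaction forward in the main analysis. State the denominator and report the number of such subjects with side and severity. Add side of face to the adverse event form.
4. Show carry-forward, and each such subject counted as worse on the side named, as sensitivity analyses only. Subjects know which side they treat, so counting every stop as worse can create false signals of harm.

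The cost is one column on three forms, one field on the adverse event form, a few lines of text and one short visit per stopper (3 in the example). No extra subjects are needed. The limits are real: the reaction may have faded by the exit visit, and the main analysis does not recover subjects who never return. Almost all the gain comes from those who do attend.

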9. FINAL SUBJECT STATUS

Study termination forms will be completed for each study subject who receives study product. This includes subjects who completed the study or who withdrew or were withdrawn from study.

9.1 COMPLETED, DISCONTINUED OR INCOMPLETE SUBJECTS

A completed subject is a subject who has satisfied all study entry criteria and completed the 2-week study. For any subject who has started study and terminates the study prematurely, efforts will be made to obtain final evaluations of clinical status. Reasonable efforts will be made to contact any subject lost to follow-up during the course of the study in order to complete assessments and retrieve any outstanding data and clinical supplies. The investigator will choose the description that best describes the status of the subject at termination.

1. Subject completed the 2-week study period

OR INCOMPLETE/DISCONTINUED DUE TO:

- 2. Contact dermatitis
- 3. Adverse experience
- 4. Serious adverse experience
- 5. Pregnancy
- 6. Protocol violation
- 7. Subject withdrew consent
- 8. Subject lost to follow-up
- 9. Other

10. STUDY PRODUCTS & ADMINISTRATION

10.1 FORMULATIONS

Subjects will apply Winlevi as currently marketed to one randomized side of the face twice daily

10.2 PRECAUTIONS

Study products should be used in their intended fashion and not orally consumed or placed in the eyes.

10.3 STUDY PRODUCT ADMINISTRATION

The subjects will apply the study products twice daily to the randomized side of the face. The study products will be labeled left and right to ensure subject compliance. The subjects will receive the following instructions: Apply twice daily to entire randomized side of face (product applied to randomized forehead, cheek, and jawline).

10.4 PACKAGING, LABELING, DISTRIBUTION

Study products will be dispensed in packaging as currently marketed provided by the sponsor.

10.5 STORAGE AND ACCOUNTABILITY OF STUDY PRODUCT

The study products will be stored at room temperature in a locked, limited access area at the study site. Only the investigator and staff members designated to dispense study medication will be allowed access to the study products. Study product logs will be used to record the dispensation and return of all study products. The subject number/initials, and the initials and date of the person dispensing and receiving the returned study products will be documented on this form.

10.6 CODE DISCLOSURE

A randomization code will be maintained indicating which side of the face received the currently marketed Winlevi. An independent blinded dispenser who is not associated with other study activities will randomize the study products and maintain the randomization until data lock occurs.

11. ADVERSE EVENTS

11.1 ADVERSE REACTIONS PREVIOUSLY REPORTED

The study products have been reported to rarely produce skin irritation.

11.2 ADVERSE EXPERIENCES

An adverse experience is defined as any untoward medical occurrence (sign, symptom or laboratory finding), regardless of severity and whether or not attributed to the study product.

The investigator/coordinator will report all adverse experiences (AEs) that occur throughout the study. All AEs will be recorded in the appropriate AE log. The report will include: date of onset, a description of the AE, severity, seriousness, action taken, relationship to the study drug, outcome of the event, and date of resolution.

11.2.1 ASSESSMENT OF SEVERITY

The intensity or severity of an AE is characterized as:Mild:AE which is easily tolerated.Moderate:AE sufficiently discomforting to interfere with daily activity.Severe:AE which prevents normal daily activities.

Subjects who are withdrawn from the study due to any AE will be followed by the investigator until the outcome is determined. The investigator will summarize and will document all information relating to the AE and follow up.

11.2.2 RELATIONSHIP TO STUDY PRODUCT

The relationship is characterized as:

Not Related - applies to any adverse experience that is clearly not related to use of the study product.

Possible - means the association of the adverse experience with the study product is unknown; however, a relationship between study product and experience cannot be ruled out.

Probable - there is a reasonable temporal relationship between the use of the study product and the adverse experience. Based upon the investigator's clinical experience, the association of the event with the study product seems likely.

Definite - The AE occurs following the application of the study product and it cannot be reasonably explained by any other known characteristics of the subject's clinical state, environmental or toxic factors, or other modes of therapy administered to the subject. It disappears or decreases upon discontinuation of the study product and reappears on a re-challenge of the study product. This is necessary to evaluate allergic or irritant contact dermatitis.

11.3 SERIOUS ADVERSE EVENTS

Definition: An SAE is defined as any adverse experience occurring that results in any of the following outcomes:

- 1. death
- 2. immediately life-threatening illness
- 3. hospitalization (>24 hours) or prolongation of existing hospitalization
- 4. a persistent or significant disability
- 5. a congenital anomaly/birth defect
- 6. "other" important medical event

These are not anticipated, however, should an SAE occur, the primary investigator ([name]) will accept responsibility to notify the sponsor.

12. STATISTICAL METHODS

Along with descriptive statistics (means, standard deviations and percentages), investigator and subject ordinal nonparametric results will be analyzed using Wilcoxon signed rank test and sign test for paired comparison at different time points. The noninvasive parametric results will be analyzed using paired t-test. Changes will be considered significant at the alpha level of 0.05.

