	immunosuppressive medications (e.g., azathioprine, belimumab,

	cyclophosphamide, Enbrel, Imuran, Humira, mycophenolate mofetil, methotrexate, prednisone, Remicade, Stelara) and/or radiation as determined by study documentation.
Endpoints:	Primary Endpoint: The primary endpoint is the change in corneometry reading between the two sides of the face treated with Winlevi versus no treatment.
	Secondary Endpoints: The secondary endpoint is the change in TEWL reading between the two sides of the face treated with Winlevi versus no treatment.
Measures:	Dermatologist Investigator assessed tolerability parameters: dryness, erythema, scaling, and irritation will be assessed separately for each side of the face. All assessments will be made on a 5-point ordinal scale (0=none, 1=minimal, 2=mild, 3=moderate, 4=severe) at baseline, 24 hours, week 1, and week 2.
	Subject assessed tolerability parameters: dryness, tightness, stinging, itching, and burning will be assessed separately for each side of the face. All assessments will be made on a 5-point ordinal scale (0=none, 1=minimal, 2=mild, 3=moderate, 4=severe) at baseline, 24 hours, week 1, and week 2.
	Noninvasive Biomeasurements : TEWL and corneometry measurements on the right and left cheek will be conducted at baseline, 24 hours, week 1, and week 2.
Statistical Methods:	Along with descriptive statistics (means, standard deviations and percentages), investigator ordinal nonparametric data will be analyzed using Wilcoxon signed rank test and sign test for paired comparison at different time points. The noninvasive parametric data will be analyzed using paired t-test. Change will be considered significant at the alpha level of 0.05.

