5. STUDY DESIGN OVERVIEW

Female or male subjects with acne prone skin will be enrolled in this split face single site study evaluating the barrier effects of Winlevi. Subjects who sign consent and meet all inclusion criteria and none of the exclusion criteria will be enrolled at the baseline visit. Subjects will be asked to continue their own, self-selected cleanser and sunscreen throughout the 2-week study with equal application to both sides of the face. The sunscreen and cleanser must have been used for 30 days prior to study enrollment without difficulty. Subjects must apply Winlevi twice daily to the randomized right or left face.

Subjects will receive a compliance diary and the blinded study treatment product to be applied to the randomized half face following cleansing, every morning and evening. The assessing dermatologist investigator will be blinded as to which side of the face is receiving the Winlevi treatment. Subjects will be seen at baseline, 24 hours, week 1, and week 2. The dermatologist investigator and subjects will assess tolerability for each side of the face separately at each visit on a 5 point ordinal scale. Noninvasive TEWL and corneometry assessments of both sides of the face will be conducted at baseline, 24 hours, week 1, and week 2.

Subjects will complete their study participation at week 2. The compliance diary and all study products will be collected at this time. Women of child bearing potential will be administered a urine pregnancy test at baseline and week 2.

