8. EFFICACY MEASURES

8.1 STUDY MEASURES

Dermatologist Investigator assessed tolerability parameters: dryness, erythema, scaling, and irritation will be assessed separately for each side of the face. All assessments will be made on a 5-point ordinal scale (0=none, 1=minimal, 2=mild, 3=moderate, 4=severe) at baseline, 24 hours, week 1, and week 2.

Subject assessed tolerability parameters: dryness, tightness, stinging, itching, and burning will be assessed separately for each side of the face. All assessments will be made on a 5-point ordinal scale (0=none, 1=minimal, 2=mild, 3=moderate, 4=severe) at baseline, 24 hours, week 1, and week 2.

Noninvasive Biomeasurements: TEWL and corneometry measurements on the right and left cheek will be conducted at baseline, 24 hours, week 1, and week 2.

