12.5 ENDPOINTS

12.5.1 PRIMARY EFFICACY ENDPOINT

The primary endpoint is the change in corneometry reading between the side of the face treated with Winlevi versus no treatment.

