12.5.2 SECONDARY EFFICACY ENDPOINT

The secondary endpoint is the change in TEWL reading between the side of the face treated with Winlevi versus no treatment.

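### The planned paired t-test can be read as a valid between-side test on change, but section 12 does not state the contrast or the visit, and it fixes a baseline slope that could be estimated at an average variance cost of about 2%

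*Combined protocol and SAP*

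**What the plan says.** Section 12 of the combined protocol and SAP gives the whole analysis of the instrument data in one sentence: "The noninvasive parametric results will be analyzed using paired t-test". Section 12.2 sets two-sided significance at 0.05. No covariate, model, pairing or visit is named.

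The contrast has to be inferred from the endpoints. Section 12.5.1 states: "The primary endpoint is the change in corneometry reading between the side of the face treated with Winlevi versus no treatment". Section 12.5.2 states: "The secondary endpoint is the change in TEWL reading between the side of the face treated with Winlevi versus no treatment". The synopsis wording is close to this and also names no visit: "The primary endpoint is the change in corneometry reading between the two sides of the face treated with Winlevi versus no treatment".

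The data are collected on both sides throughout. Section 8.1 states: "TEWL and corneometry measurements on the right and left cheek will be conducted at baseline, 24 hours, week 1, and week 2". The case report form in Appendix I has a box for each cheek at each of these visits. The side is randomised. Section 5 states: "Subjects must apply Winlevi twice daily to the randomized right or left face". Section 10.6 states: "A randomization code will be maintained indicating which side of the face received the currently marketed Winlevi". Neither section gives an allocation ratio.

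**The concern.** Three analyses fit the words of section 12: a between-side t-test on change from baseline, a between-side t-test on follow-up readings, and a within-side t-test of follow-up against baseline. The third would not address the endpoint. Of the other two, the first fits the word change in the endpoints better. It gives the baseline side difference a slope of exactly 1, while a follow-up test gives it a slope of 0. Nothing in the documents justifies either value, and the data to estimate the slope are already collected.

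Two things are at stake. The first is precision. The objective in section 4 is to show that Winlevi does not damage the barrier, so the width of the interval for the side difference matters, and section 12.1 gives no calculation behind the 50 subjects. The second is pre-specification. With three follow-up visits and no primary one, the visit to report could be chosen after the results are seen.

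**Working it through.** **Inputs from the documents.** 50 subjects (6.2, 12.1); two-sided 0.05 (12.2); both cheeks read at baseline and at three later visits (8.1); side randomised (5, 10.6). No SD, correlation, effect size, power or dropout rate is given, so there is no figure of the plan to reproduce.

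**Assumptions.** D is the Winlevi-side reading minus the untreated-side reading. ρ is the correlation between baseline D and follow-up D, and k is the follow-up SD of D divided by its baseline SD. Both are assumed and shown over a range. D is taken as bivariate normal with an expected baseline value of zero.

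**Variances** (baseline SD = 1, each divided by n):
- change score: 1 + k² − 2ρk
- follow-up only: k²
- slope estimated, effect read at baseline D = 0: k²(1 − ρ²)(1 + 1/(n − 3))

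**Ceiling on the average cost.** (1 + k² − 2ρk) − k²(1 − ρ²) = (1 − kρ)², which is never negative. The ratio of adjusted to change-score variance therefore cannot exceed 1 + 1/(n − 3). At n = 50 this is 48/47 = 1.021; at n = 40 it is 1.027. The same bound holds against the follow-up test.

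**Ratios at n = 50, k = 1.** Against change the ratio is ((1 + ρ)/2)(48/47); against follow-up it is (1 − ρ²)(48/47). Half-widths are simulated mean 95% CI half-widths in SDs of D.

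| ρ | adjusted / change | half-width, change | half-width, adjusted | adjusted / follow-up |
|---|---|---|---|---|
| 0 | 0.51 | 0.400 | 0.286 | 1.02 |
| 0.3 | 0.66 | 0.335 | 0.273 | 0.93 |
| 0.5 | 0.77 | 0.283 | 0.247 | 0.77 |
| 0.7 | 0.87 | 0.219 | 0.204 | 0.52 |
| 0.9 | 0.97 | 0.126 | 0.125 | 0.19 |

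Simulation with 40,000 trials per row gave 0.517, 0.662, 0.769, 0.871 and 0.972 against change, with type I error of 0.047 to 0.051 for all three tests. Break-even against change is ρ = 2 × 47/48 − 1 = 0.96. Over the same ρ values, the ratio to the change score is 0.40–0.64 for k = 0.8 and 0.62–1.00 for k = 1.25.

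**Spread around the average cost.** In one trial the variance factor is 1 + n × (mean baseline D)² / (sum of squares of baseline D about its mean). The excess is distributed as F(1, 49)/49. Its mean is 0.021 and its 95th percentile about 0.082, so the factor exceeds 1.08 in about 5% of trials.

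**Treated side.** The intercept needs an expected baseline D of zero. Take an assumed stable left-right offset of 0.5 SD, ρ = 0.5 and no treatment effect. At 25:25 there is no bias. At 30:20 the adjusted intercept is off by 0.04 SD, follow-up only by 0.10, and the change score by 0. Adding treated side coded −1/2 and +1/2 brings the adjusted bias to 0. It costs about nothing at 25:25, about 2% under simple randomisation, and 1/(1 − 0.2²) = 1.04, or 4%, at 30:20.

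**Visit.** If any of three equally correlated visits could be claimed at 0.05, the chance of at least one false significant difference is 0.136, 0.126, 0.110 and 0.083 at assumed correlations of 0.3, 0.5, 0.7 and 0.9.

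**Carry-forward.** Section 8.3 states: "Subjects who are noncompliant will be released from their study participation and their last visit data carried forward". If baseline is carried forward at random in 10% of subjects, the ratios to change are 0.56, 0.70, 0.80, 0.89 and 0.98, with type I error of 0.047 to 0.052. A true effect of 0.40 SD then averages 0.36 under all three methods.

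**The case against.** The strongest reply is that this is a preference about efficiency. The t-test is valid, change from baseline already uses the baseline reading, and the gain depends on a correlation that nobody has stated. That stands. On the natural reading of the endpoint, the gain is 13% of variance at ρ = 0.7 and 3% at 0.9. The large ratios in the last column of the table apply only to the less likely follow-up reading.

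It is also fair that 2% is an average and that treated side adds to it. Under simple randomisation the two covariates together cost at most about 1.021 × 1.02 = 1.04 on average; at 30:20, about 1.021 × 1.04 = 1.06. The change score avoids the offset bias without any covariate. A rule that adds treated side only when the split is uneven would leave the model open, because an exact 25:25 split occurs in only 11% of trials under simple randomisation. The covariate should therefore always be included.

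The carry-forward check is narrow. Section 8.3 allows that noncompliance may come from problems with the product, and the last visit carried may be 24 hours or week 1. The check says nothing about carry-forward that is not at random.

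The 8–14% counts differences in either direction. For an objective of no damage, the more telling risk is choosing a visit that shows no difference, which this figure does not measure. It does not remove the need to name a visit.

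**Conclusion.** The point holds as something to consider. Section 12 leaves the contrast and the visit unstated and forgoes an adjustment whose data are already collected. Under the normal model, the ceiling of about 2% on the average cost of the baseline covariate at n = 50 is firm. The gain over the change score ranges from about 49% of variance at ρ = 0 to 3% at ρ = 0.9 with equal SDs, and the documents do not place this trial within that range.

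A reader might infer three stronger things that the documents do not support:
- That the planned test is wrong. With randomised sides, a between-side t-test at one visit keeps its 5% error rate.
- That this trial will gain a stated amount of precision. No correlation or SD is given.
- That a narrower interval would establish the absence of barrier damage. No margin is stated, and precision does not replace one.

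The missing visit and the unstated contrast need settling whether or not the covariate is adopted.

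**What to change.** Put the following in section 12:

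> For corneometry (primary) and TEWL (secondary), D is the reading on the Winlevi side minus the reading on the untreated side. D at one pre-specified visit, named here by the sponsor, is regressed on baseline D and treated side (left/right, coded −1/2 and +1/2, always included whatever the achieved split). The treatment effect is the intercept at baseline D = 0, with baseline D not centred at its sample mean, reported with its 95% CI and two-sided p-value. Other visits are supportive, and within-side changes from baseline are descriptive.

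Baseline D must stay uncentred, because centring it at the sample mean removes the baseline adjustment from the intercept.

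If the sponsor prefers the t-test, it remains valid. Section 12 should then say that it compares the two sides, whether it uses change from baseline or follow-up readings, and at which visit.

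The cost is a few sentences, one regression and two degrees of freedom, with no new data or visits.
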